9.4.3.2 Safety

The analysis of reactogenicity will be based on the DS while the analysis of other safety endpoints such as unsolicited events will be based on the ES. The following analysis will be generated for each vaccine group.

Solicited administration site and systemic endpoints

The following summaries will be generated for any grade ([Table 13](#)), grade ≥ 2 , grade ≥ 3 , medically attended, ongoing after day 7:

- Occurrence of at least one solicited administration site event during a 7-day follow-up period (i.e., day of vaccination and 6 subsequent days) after each vaccination and overall.
- Occurrence of at least one solicited systemic event during a 7-day follow-up period (i.e., day of vaccination and 6 subsequent days) after each vaccination and overall.
- Duration of each solicited AE starting on the day of vaccination or on one of the 6 subsequent days will be summarized after each vaccination and overall.

Frequencies and percentages of participants experiencing each event will be presented for each vaccination and across vaccinations with Clopper-Pearson exact 95% CIs.

If a solicited event occurs more than once for a participant, it will be counted in the summary only once for each level of summarization, according to the maximal severity.

Laboratory endpoints

The percentage of participants with an increase in laboratory toxicity grading after each vaccination and across vaccinations will be provided with Clopper-Pearson exact 95% CIs.

This will be done for each safety laboratory test and across laboratory tests for exposed participants with safety laboratory results available after vaccination.

Unsolicited AE and MAE endpoints

- Occurrence of unsolicited AEs within 21 days (day of vaccination and 20 subsequent days) after each vaccination and overall.
- Occurrence of MAEs within 21 days (day of vaccination and 20 subsequent days) after each vaccination and also through 6 months post dose 2.

SAE/pIMD endpoints

- Occurrence of SAEs and pIMDs up to Visit 5 (Day 43) and also through 6 months post dose 2.

The original verbatim terms used by investigators to identify AEs in the eCRFs will be mapped to preferred terms (PTs) using the Medical Dictionary for Regulatory Activities (MedDRA). The AEs will then be grouped by Medical Dictionary for Regulatory Activities PTs into frequency tables according to system organ class.

For each of the unsolicited AE, SAE, and pIMD endpoints the number of participants and percentage will be summarized regardless of MedDRA classification and by system organ class and by preferred term within system organ class for each study group.

Separate summaries will be produced for the following categories:

- AE of any grade
- AEs of any grade that are possibly or probably related to vaccine(s)
- Grade 3 AE
- Grade 3 AE that are possibly or probably related to vaccine(s)
- MAE of any grade
- pIMDs
- SAEs
- SAEs related to vaccine
- Fatal SAE
- Fatal SAE related to vaccine

Data listings of all AEs will be provided by participant. In addition, AEs in the categories above will be provided as listed data.

9.4.4 Secondary Endpoint(s) Analysis**9.4.4.1 Immunogenicity**

Secondary immunogenicity analyses will be based on the PPS.

Geometric mean titers with associated 95% CI will be calculated for each study group for vaccine-homologous H5N8 HI titer at Days 1, 22, and 6 months post dose 2. Geometric mean fold rise increase compared to pre-vaccination and associated 95% CI will be calculated at Days 22, and 6 months for each study group for vaccine-homologous H5N8 HI antibody titer. The GMT and GMFR CIs will be derived from an ANCOVA model on log-transformed titer. The model will include the dose group effect (i.e., 4 dose groups), as a fixed effect and the log -transformed titer pre-dose 1 (Day 1) as a covariate.

The following aggregate variables will be calculated for each study group for vaccine-homologous H5N8 HI antibody titer along with Clopper-Pearson exact two-sided 95% CIs:

- SCR at Day 22, Day 43, and 6 months post dose 2, and
- SPR at Day 1, 22, and 6 months post dose 2.

For a subset of participants with Microneutralization (MN) antibody titers, the following aggregate variables will be calculated for each study group for vaccine-homologous H5N8 MN antibody titer:

- GMTs at Days 1, 22, 43, and 6 months post dose 2
- Seropositivity rates at Days 1, 22, 43, and 6 months post dose 2
- VRR at Days 22, 43, and 6 months post dose 2

The GMTs with 95% CIs will be tabulated by visit for each study group. For seropositivity/VRR, percentage of participants will be calculated with Clopper-Pearson exact two-sided 95% CIs.

9.4.5 Demography and Baseline Characteristic Analyses

Demographic characteristics (age, gender, race, center, country, ethnicity, and occupation) will be tabulated per study group for ES and PPS, as described in the SAP.

For continuous characteristics, mean, range, and standard deviation will be calculated.

For discrete variables, distribution, and associate frequency will be calculated.

Listings will be provided for demographic characteristic data based on the enrolled set.

9.5 Interim Analysis

An interim analysis will be performed on data collected through the Day 43 visit. This interim analysis will provide treatment-level unblinded summaries for GSK, and BARDA, and no individual unblinding data will be provided. The details of the interim analysis are provided in Section 9.5.1 and will be fully detailed in the SAP.

9.5.1 Sequence of Analyses

9.5.1.1 *Interim Safety Analysis at Day 43*

An analysis will be performed on data collected through the Day 43 visit. Elements will include:

- Analyses of cleaned solicited administration site events and solicited systemic events data collected during a 7-day follow-up period (i.e., day of vaccination and 6 subsequent days) after each vaccination.
- Analyses of unsolicited AEs reported up to the Day 43 visit (i.e., day of vaccination and 20 subsequent days after each vaccine) and cleaned in so far as is possible.
- Analyses of SAEs, pIMDs, MAEs, pregnancies, and withdrawals due to AEs, collected up to the Day 43 visit.
- No study report will be prepared. Access to individual treatment codes will be restricted to the designated statisticians in charge of the analysis. No individual listings or data with the participants' identifying information will be disseminated. Listings of final data will be provided with the EOS report.

9.5.1.2 *Interim Immunogenicity Analysis at Day 43*

An analysis will be performed on data collected through the Day 43 visit. Elements will include:

- Analyses of cleaned immunogenicity data, for analysis of vaccine-homologous HI antibody titers and MN titers, collected through the Day 43 visit.
- Results will be presented in a Day 43 statistical report. Access to individual treatment codes will be restricted to the designated statisticians in charge of the analysis. No individual listings or data with the participants' identifying information will be disseminated. Listings of final data will be provided with the EOS report.

All analyses will be performed on data that has been cleaned and locked. The possibility of post-analysis changes to data evaluated at Day 43 exists, since data collection and data entry

may continue through 6 months post dose 2. All final data will be presented in the listings provided at 6 months post dose 2.

9.5.1.3 *Final Analysis (6 Months Post Dose 2)*

A final data analysis will be performed at the EOS (6 months post dose 2) of all primary and secondary endpoints based on the clean data, including evaluations of:

- Immunogenicity at all measured time points.
- Solicited administration site events and solicited systemic events data reported within 7 days after each vaccination (day of vaccination and 6 subsequent days following each vaccination).
- Unsolicited AEs reported up to the Day 43 visit (day of vaccination and 20 subsequent days after each vaccination).
- Concomitant medications reported up to the Day 43 visit.
- SAEs, pIMDs, MAEs, and withdrawals due to AEs collected throughout the entire study.
- Pregnancies throughout the entire study. An integrated clinical study report containing all data will be written and made available to the investigators.

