1.3 Schedule of Activities

Table 1 Schedule of Activities

Time points	Screening Visit	Visit 1 ¹ Day 1 Dose 1	Visit 2 ² Day 8-10	Visit 3 ¹ Day 22 Dose 2	Visit 4 ² Day 29-31	Visit 5 Day 43	Visit 6/EOS 6 months post dose 2
Informed consent	•						
Check inclusion/exclusion criteria	•	•		•			
Collect demographic data	•						
Study group and treatment number allocation		0					
Treatment number allocation for subsequent dose				0			
Recording of administered treatment number		•		•			
Blood sampling for hematology and biochemistry safety tests (approx. 10 mL for screening and approx. 6 mL for post-vaccination tests) ³	•		• ²		• ²		
Blood sampling for immunogenicity assessments and HI/MN assay development/validation and samples for BARDA ⁴ (40 mL)		• ¹		• ¹		•	•
Vaccine administration		•		•			
30-minute observation period after each vaccine administration		•		•			
Medical history	•	•					
Physical examination ⁵	•						
Vaccination history	•	•					
Urine pregnancy test to be performed prior to each vaccination (women of childbearing potential only)		•		•			
Check contraindications and warnings and precautions to vaccination		•		•			
Pre-vaccination body temperature		•		•			

Time points	Screening Visit	Visit 1 ¹ Day 1 Dose 1	Visit 2 ² Day 8-10	Visit 3 ¹ Day 22 Dose 2	Visit 4 ² Day 29-31	Visit 5	Visit 6/EOS 6 months post dose 2
Record any concomitant medication/vaccination	•	•		•		•	•
Distribution of diary cards		0		0			
Recording of solicited events (Up to 7 days after each vaccination)		•		•			
Recording of unsolicited adverse events (Up to 21 days after each vaccination)		•	•	•	•	•	
Return of diary cards			0	0	0	0	
Diary card transcription by investigator or delegate			• ⁶	•	• ⁶	•	
Reporting of SAEs, pIMDs, MAEs, pregnancies		•	•	•	•	•	•
Study Conclusion							•

Abbreviations: BARDA=Biomedical Advanced Research and Development Authority; eCRF=electronic case report form; EOS=end of study; FDA=Food and Drug Administration; HI=hemagglutination inhibition; MAE=medically attended adverse event; MN=microneutralization; pIMD=potential immune-mediated disease; SAE=serious adverse event.

Note: the double-line borders indicate analyses which will be performed on all data obtained up to those time points.

• is used to indicate a study procedure that requires documentation in the individual eCRF.

0 is used to indicate a study procedure that does not require documentation in the individual eCRF.

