¹ All Day 1 and Day 22 activities, including blood draw, are to be performed prior to vaccine administration.

² The first 50% of study participants in each age and dose group will be required to have safety laboratory assessments performed at the clinic 7-days post each vaccination (i.e., Visit 2 and Visit 4). All other participants will have a remote visit (e.g., telephone call, video call, email, or text communication) with the site.

³ See [Table 10](#) for applicable laboratory assessments.

⁴ Participant will be asked in Informed Consent Form for permission for future use of blood samples, including use by BARDA.

⁵ A physical examination based on medical history will be performed at the Screening Visit. Physical examination at each study visit after the study intervention administration visit will be performed only if the participant/participant's caregiver(s) indicates during questioning that there might be some underlying pathology(ies) or if deemed necessary by the investigator or delegate.

⁶ Participants required to have safety laboratory measurements at Visits 2 and 4 will also have the initial data from their diary cards transcribed and then the diary card returned to them during these visits. All other participants will return their diary cards and have them transcribed on Visits 3 and 5.

Table 2 Interval Between Study Visits

Interval	Planned visit interval	Allowed interval range
Screening → Visit 1	Up to 14 days	14 days
Visit 1 → Visit 2	7 days	7-9 days
Visit 1 → Visit 3	21 days	14-35 days
Visit 3 → Visit 4	7 days	7-9 days
Visit 3 → Visit 5	21 days	14-35 days
Visit 3 → Visit 6	180 days post dose 2	165-195 days

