3.0 OBJECTIVES, AND ENDPOINTS

Objectives	Endpoints (Population Summary)
Primary	

Immunogenicity:
 
To evaluate whether the monovalent influenza A/Astrakhan/3212/2020-like (H5N8) virus vaccine containing 3.75 µg, or 7.5 µg of HA with AS03_A or AS03_B elicits a HI response to the vaccine-homologous virus that meets or exceeds the US Food and Drug Administration, Center for Biologics Evaluation and Research immunogenicity criteria at the Day 43 visit.
	
Humoral immune response in terms of:
 
 • Vaccine-homologous HI titers at Day 43 (i.e., GMT). • Vaccine-homologous HI titers increase at Day 43 compared to pre-vaccination (i.e., GMFR). • SP defined as titer $\geq 1:40$ at Day 43 (percentage of participants meeting SP criteria).

Safety:
 
To evaluate the safety and reactogenicity of the different vaccine formulations through the Day 43 visit and SAEs and pIMDs through Day 43 and also to 6 months post dose 2
	
 • Occurrence of each solicited administration site event during a 7-day follow-up period (i.e., day of vaccination and 6 subsequent days) after each vaccination (percentage of participants with occurrence). • Occurrence of each solicited systemic event during a 7-day follow-up (i.e., day of vaccination and 6 subsequent days) after each vaccination (percentage of participants with occurrence). • Occurrence of toxicity grade increase in either hematology or biochemistry laboratory tests 7 days after each vaccination (percentage of participants with change from baseline). • Occurrence of unsolicited AEs for 21 days (i.e., day of vaccination and 20 subsequent days) after each vaccination (percentage of participants with occurrence). • Occurrence of MAEs for 21 days (i.e., day of vaccination and 20 subsequent days) after each vaccination and also through 6 months post dose 2 (percentage of participants with occurrence). • Occurrence of SAEs until Day 43 and also 6 months post dose 2 (percentage of participants with occurrence). • Occurrence of pIMDs until Day 43 and also 6 months post dose 2 (percentage of participants with occurrence).

Objectives	Endpoints (Population Summary)
Secondary	

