9.5.2 Statistical Consideration for Interim Analysis

Since the primary endpoints for the study will be complete by the Day 43 visit (collection past Day 43 includes only assessments for SAEs, pIMDs, MAEs, and immunogenicity at 6 months post dose 2), no statistical consideration for multiplicity will be given to account for changes in the results reported at the interim analysis compared to the final analysis. For the primary immunogenicity analysis, which will be reported at Day 43 the overall type I error rate is fixed at 2.5% and a Bonferroni adjustment will be applied to allow simultaneous multiple comparisons of each antigen/adjuvant group leading to 0.625% nominal type I error. For the primary safety analyses no adjustment for multiple comparisons will be made in each antigen/adjuvant group.

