## 4.2. Interim Analysis

The interim analysis, including reactogenicity, safety and immunogenicity data, is planned when data collected through to, and including, the Day 43 visit, is available for all participants.

### 4.2.1. Interim Safety Analysis at Day 43

An analysis will be performed on data collected through the Day 43 visit. Elements will include:

- Analyses of cleaned solicited administration site events and solicited systemic events data collected during a 7-day follow-up period (i.e., day of vaccination and 6 subsequent days) after each vaccination.
- Analyses of unsolicited AEs reported up to the Day 43 visit (i.e., day of vaccination and 20 subsequent days after each vaccine) and cleaned in so far as is possible, will be carried out.
- Analyses of SAEs, pIMDs, MAEs, pregnancies, and withdrawals due to AEs, collected up to the Day 43 visit, will be carried out.
- No study report will be prepared. Access to individual treatment codes will be restricted to the designated statisticians in charge of the analysis. No individual listings or data with the participants' identifying information will be disseminated. Listings of final data will be provided with the EOS report.

### 4.2.2. Interim Immunogenicity Analysis at Day 43

An analysis will be performed on data collected through the Day 43 visit. Elements will include:

- Analyses of cleaned immunogenicity data, for analysis of vaccine-homologous HI antibody titers and MN titers, collected through the Day 43 visit will be conducted.
- Results will be presented in a Day 43 statistical report. Access to individual treatment codes will be restricted to the designated statisticians in charge of the analysis. No individual listings or data with the participants' identifying information will be disseminated. Listings of final data will be provided with the EOS report.

All analyses will be performed on data that has been cleaned and locked. The possibility of post-analysis changes to data evaluated at Day 43 exists, since data collection and data entry may continue through 6 months post dose 2. All final data will be presented in the listings provided at 6 months post dose 2.

---

Document: \\ieedc-vnasc01\BIOSdata\GSK\H5N8(Flu)\HAB99808\Biostatistics\Documentation\SAP\SAP\SAP v5.0\GSK H5N8-219833\_SAP\_v5.0\_19AUG2024.docx

Author: PPD Version Number: 5.0

Version Date: 19AUG2024

Template No.: CS\_TP\_BS016 Revision 7

Reference: CS\_WI\_BS005

Effective Date: 01Nov2021

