## 6.4. Windowing Conventions

Allowed time window for each visit will be performed as mentioned in “Schedule of Activities”, section 1.3 of protocol. Intervals between study visits are included in [Table B](#) and window conventions are included in

---

Document:	\ieedc-\vnasc01\BIOSdata\GSK\H5N8(Flu)\HAB99808\Biostatistics\Documentation\SAP\SAP\SAP\SAP v5.0\GSK H5N8-219833_SAP_v5.0_19AUG2024.docx		
Author:	PPD	Version Number:	5.0
		Version Date:	19AUG2024
Template No.:	CS_TP_BS016 Revision 7		
Effective Date:	01Nov2021		
Reference:	CS_WI_BS005		

**Table C.** In case vaccination or lab sample planned at a visit was made on another day, the same interval window will be used for the actual vaccination/lab sample date.

In protocol amendment 3.0 version the visit interval windows have been updated for Visit 1 → Visit 3 and Visit 3 → Visit 5, from 14-28 days to 14-35 days. The window visits have been extended due to the large number of participants whose Visit 3 or Visit 5 was out of window due to the enrolment hold. The Window convention in table C are updated accordingly.

Table B: Intervals between Study Visits

Interval	Planned visit interval	Allowed interval range
Screening → Visit 1	Up to 14 days	14 days
Visit 1 → Visit 2	7 days	7-9 days
Visit 1 → Visit 3	21 days	14-35 days
Visit 3 → Visit 4	7 days	7-9 days
Visit 3 → Visit 5	21 days	14-35 days
Visit 3 → Visit 6	180 days post dose 2	165-195 days

---

Document:	\\ieedc-vnasc01\BIOSdata\GSK\H5N8(Flu)\HAB99808\Biostatistics\Documentation\SAP\SAP\SAP v5.0\GSK H5N8-219833_SAP_v5.0_19AUG2024.docx
Author:	PPD
	Version Number: 5.0
	Version Date: 19AUG2024

Template No.: CS\_TP\_BS016 Revision 7

Reference: CS\_WI\_BS005

Effective Date: 01Nov2021

Table C: Window convention

Assigned Study Day	Visit label as per protocol	Visit assigned
Day 1	Visit 1	Visit 1 (Day 1)
Day 8	Visit 2	Visit 2 (Day 8-10)
Day 22	Visit 3	Visit 3 (Day 15-36)
Day 29	Visit 4	Visit 4 (Day 22-45)
Day 43	Visit 5	Visit 5 (Day 29-71)

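### Visit 5 may fall as early as 14 days after dose 2, yet it is the last scheduled point for recording unsolicited AEs, so the 21-day safety window after dose 2 can be cut short by up to 6 days without being flagged

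*Protocol*

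**What the plan says.** **Endpoint.** Protocol section 3.0 lists as a primary safety endpoint "Occurrence of unsolicited AEs for 21 days (i.e., day of vaccination and 20 subsequent days) after each vaccination (percentage of participants with occurrence". The window is therefore 21 calendar days, days 0 to 20 after each dose.

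**Visit window.** Protocol Table 2 and SAP Table B allow 14 to 35 days from Visit 3 (dose 2) to Visit 5, with 21 planned. SAP 6.4 records that the windows were "updated for Visit 1 → Visit 3 and Visit 3 → Visit 5, from 14-28 days to 14-35 days". The upper limit moved and the lower limit did not.

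**Collection schedule.** The Table 1 row "Recording of unsolicited adverse events (Up to 21 days after each vaccination" is marked up to Visit 5 and is blank at Visit 6. Protocol 9.5.2 states that "collection past Day 43 includes only assessments for SAEs, pIMDs, MAEs, and immunogenicity at 6 months post dose 2". Visit 6 is 165–195 days after dose 2, and no contact is scheduled in between.

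**Analysis text.** Protocol 9.5.1.3 lists "Unsolicited AEs reported up to the Day 43 visit (day of vaccination and 20 subsequent days after each vaccination", and 9.5.1.1 has its interim counterpart. SAP 4.2.1 repeats it: "Analyses of unsolicited AEs reported up to the Day 43 visit (i.e., day of vaccination and 20 subsequent days after each vaccine".

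**Denominator.** Unsolicited AEs are summarised in the Exposed Set, which is everyone who received a study intervention (protocol Table 9). SAP 16.1.2 plans a crude percentage with an exact 95% CI. For this endpoint the SAP 2.4 estimand table lists only permanent study discontinuation before Day 21 as an intercurrent event, and it rules out imputation.

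**Text on the other side.** Protocol 8.5.1 requires every unsolicited AE within 21 days of each dose to be entered in the eCRF, with no link to visit date. Protocol 10.5.1 tells participants to contact the site about MAEs and events that concern them, and leaves the remaining events to an interview and record review at the next visit.

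**The concern.** The analysis sections use a visit as a stand-in for a fixed number of days. That works if Visit 5 is at about day 20 after dose 2 or later. It fails for a visit that is early but in window, and such a visit is not a protocol deviation, so deviation review would not flag it.

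The events exposed to loss are non-serious, not medically attended and not pIMDs, with onset between an early Visit 5 and day 20 after dose 2. SAEs, pIMDs and MAEs are collected to 6 months, so those endpoints are not affected. The dose 1 window is not affected either, because Visits 4 and 5 follow it and Visit 5 is at least 28 days (14 + 14) after dose 1.

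At stake is a one-directional error in a primary safety endpoint. An event that is not recorded lowers the numerator, while the participant stays in the Exposed Set denominator. Nothing planned in the SAP would show a reader how often this happened.

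**Working it through.** **Step 1. Reproduce the plan's visit windows.** The inputs are the intervals in protocol Table 2, with dose 1 on Day 1.

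- Visit 3: 1 + 14 to 1 + 35 = Day 15–36.
- Visit 4: 15 + 7 to 36 + 9 = Day 22–45.
- Visit 5: 15 + 14 to 36 + 35 = Day 29–71.

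All three match SAP Table C, so a Visit 5 at 14 days after dose 2 is in window by the plan's own figures.

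**Step 2. Days of the window without scheduled collection.** Let d be the days from dose 2 to Visit 5. If the visit day counts as observed, covered days = min(d + 1, 21) and lost days = 21 − covered days.

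| d | Covered | Lost | Lost, % of 21 |
|---|---|---|---|
| 14 | 15 | 6 | 28.6 |
| 15 | 16 | 5 | 23.8 |
| 16 | 17 | 4 | 19.0 |
| 17 | 18 | 3 | 14.3 |
| 18 | 19 | 2 | 9.5 |
| 19 | 20 | 1 | 4.8 |
| 20 or more | 21 | 0 | 0 |

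Six of the 22 permitted values of d (14 to 35) lose at least one day. If the visit day does not count as observed, each of those six loses one day more, and d = 20 loses one day.

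**Step 3. Effect on the percentage.** The documents give no unsolicited-AE rate, no share of early visits and no onset pattern, so this step rests on assumptions. Take a true 21-day incidence p = 20%, a constant hazard and no capture after Visit 5. With k covered days:

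observed incidence = 1 − (1 − p)^(k/21)

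For k = 15, 16, 17, 18, 19, 20 this gives 14.7, 15.6, 16.5, 17.4, 18.3 and 19.1%, with a mean of about 17.0%. Early attenders spread evenly over days 14–19 therefore read about 3.0 points low.

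If a share f of a group attends early, group bias = f × 3.0 points:

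- f = 10%: 0.3 points, so 20% reads as 19.7%.
- f = 30%: 0.9 points, so 20% reads as 19.1%.

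In observation time, the mean loss is (6 + 5 + 4 + 3 + 2 + 1)/6 = 3.5 days. That is 3.5/21 = 16.7% of the window for early attenders, and 1.7–5.0% for the whole group at f = 10–30%.

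**Step 4. Range.** The extreme case has every early attender at day 14. A true 20% then reads 14.7% in those participants. The group figure is 19.5, 18.7 or 17.4% if they make up 10, 25 or 50% of it. If instead events cluster soon after vaccination and only 5–10% fall in the lost days, 20% reads as 19–18% in early attenders, and the group effect is smaller again.

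**The case against.** The strongest reply is that the protocol already requires these events to be recorded. Section 8.5.1 sets a 21-day duty that does not depend on visit date, and 10.5.1 supplies two routes: participants contact the site about events of concern, and the rest are picked up by interview and record review at the next visit. Visit 6 also records concomitant medication, with reason for use and dates (Table 1; protocol 6.8). Protocol 9.5.1.2 accepts that data entry may continue to 6 months, and SAP 16.1.2 defines the summary by the 21-day period.

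Much of this stands. A reader might infer that no procedure at all captures events after an early Visit 5, and the documents do not support that. What is missing is a scheduled prompt. For an early attender the next visit is about five months later, Table 1 schedules no unsolicited-AE recording there, and 9.5.2 says such collection has ended. Read literally, the analysis text would also drop events reported after the visit.

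Three other inferences go too far:

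- **Diary return ends collection.** Footnote 6 to Table 1 says "All other participants will return their diary cards and have them transcribed on Visits 3 and 5". But the diary serves mainly the 7-day solicited events, which a day-14 visit covers in full. Unsolicited AEs are gathered by site contact and interview, so diary return does not itself truncate the endpoint.
- **Capture differs by site.** The documents give no visit timing by site. Assignment is randomised and observer-blind, so there is no reason to expect early attendance to depend on group, and SAP section 16 plans no between-group safety comparison.
- **Early attenders are declared fully observed.** No text says this. It follows only indirectly, from the Exposed Set definition and the absence of any flag for short observation.

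The size argument also carries weight. For 13 of 65 participants (20%) the exact 95% CI is 11.1–31.8%, far wider than a bias of 0.3–0.9 points. The only evidence on timing, in SAP 6.4, concerns out-of-window visits after an enrolment hold, and the response was to raise the upper limit alone.

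**Conclusion.** The point holds as a mismatch between the endpoint window and the collection schedule. The analysis text in protocol 9.5.1.1, 9.5.1.3 and SAP 4.2.1 equates two periods that differ for any Visit 5 on days 14–19 after dose 2. Table 1 and 9.5.2 conflict with the recording duty in 8.5.1. The post-dose-2 and overall unsolicited-AE percentages can be biased low, and the SAP plans nothing that would show by how much.

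The size is unknown and probably small: about 0.3–0.9 points on a true 20%, assuming that 10–30% attend evenly on days 14–19, that hazard is constant, that the visit day counts as observed and that nothing is captured late. Early clustering of events or any late capture would reduce it. A larger early share, or visits concentrated at day 14, would increase it. The documents do not support a claim that the primary safety endpoint is materially distorted. The correction is still worth making, because the error has one direction and the dates needed to measure it are already collected.

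**What to change.** 1. **Reconcile the collection text.** Bring protocol Table 1 and 9.5.2 into line with 8.5.1, so that recording of unsolicited AEs is tied to 21 days after each dose and not to the date of Visit 5.
2. **Define analysed events by onset.** In protocol 9.5.1.1 and 9.5.1.3 and in SAP 4.2.1, replace the visit-based cut-off with onset on day 0 to day 20 after a dose, whenever the event was reported.
3. **Show the shortfall.** In SAP 16.1.2, tabulate by group how many participants had fewer than 21 days of unsolicited-AE collection after dose 2, and repeat the percentage in those with complete collection.
4. **Where still possible, add a contact.** For any participant not yet past day 20 after dose 2 whose Visit 5 was earlier, make one remote contact on or after day 20. Remote contact is already used at Visits 2 and 4. The amendment describes many Visits 3 and 5 as already out of window, so this step may come too late for some or all participants. Items 1 to 3 do not depend on it.

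The cost is a few wording changes and one extra table, using the dose 2 and Visit 5 dates that the window checks already need. Any remaining remote contacts would be few and short. The immunogenicity windows do not change.
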